3.1.3 Exclusion Criteria

The exclusion criteria of the study are:

1. Known allergy to any of the protocol-stipulated treatments, or non-tolerance of multilayer, multicomponent compression therapy intended for the treatment of VLU.
2. History of significant haematological disorders (e.g. Sickle Cell disease).
3. History of Deep Vein Thrombosis (DVT) within six months preceding study entry (i.e. RV1).
4. History of Pyoderma Gangrenosum or other inflammatory ulceration.
5. Pregnancy or breast feeding.
6. Use of investigational drug or device within four weeks prior to study entry (i.e. RV1) that may interfere with this study.
7. Use of any neuro-modulation device.
8. Surgery during three months preceding study entry (such as abdominal, gynaecological, hip or knee replacement) (i.e. RV1).
9. Trauma to the lower limbs that would prevent geko™ from stimulating the common peroneal nerve.
10. No involuntary movement of the lower leg/foot at the maximum tolerable device setting.
11. Any medication deemed by the Investigator to potentially interfere with the study treatment (e.g. systemic steroids.)

12. Participation in any other clinical study.

4 Study Schedule

The study is divided into three phases: the Run-in Phase, the Treatment Phase and Follow-up Phase. The schedules for the protocol-specified assessments and procedures in each phase are detailed below in the following sections.

One week equals 7 days and the allowed visit window is one week \pm 3 days. Every attempt should be made to maintain participants on their original weekly treatment schedule. When determining the visit dates, the reference should always be to the RV1 or TV1 date and not the participant's previous visit.

There will be a Healing Confirmation Visit (HCV) scheduled in a minimum 7 days for participants who present with 100% re-epithelialisation without drainage of the study ulcer as determined by the PI or designee during the Treatment Phase.

4.1 Run-in Phase

Investigators should confirm that the patient has provided written informed consent. Thereafter procedures during the Run-in Phase should be performed in the following order:

- Confirm Participant response to gekoTM treatment by presence of involuntary movement of the lower leg/foot at the maximum tolerable device setting (RV1 only).
- Measure ABPI if a valid ABPI reading has not taken within 8 weeks of RV1
- Confirm eligibility (RV1 only). If the patient is not eligible, discharge the patient from the study as a screen failure. If the patient is eligible continue with the following procedures:
 - Record medical history and study ulcer history (RV1 only).
 - Administer the CWIS and EQ-5D-5L questionnaires in the participant's primary language (RV1 only).
 - Perform physical examination and assess Body Mass Index (BMI) (RV1 only).
 - Assess concomitant medications (Con Med) and update Con Med page in case report form [CRF] as appropriate).
 - Assess compression bandaging (See Section 9.8).
 - Record study ulcer location, history and duration (RV1 only).

Note: 'Study ulcer location' is defined by the ulcer being on the left or right leg, by the location of the ulcer on the malleolus, low gaiter or high calf, and by the positioning of the ulcer as lateral, medial, anterior or posterior.

- Administer the study ulcer pain VAS assessment.
- Determine Venous Clinical Severity Score (RV1 only)
- Assess for AEs. Any AEs occurring during the Run In Phase are to be recorded on an AE form
- Cleanse the study ulcer.
- Obtain a digital image of the study ulcer (if debridement is planned, this is the Pre-debridement image). N.B., all study ulcer measurements will be performed using the pre-debridement images.

- At the discretion of the Investigator, perform debridement of the study ulcer to obtain a clean, granulating ulcer base with minimal adherent slough.
- If applicable, obtain a post-debridement digital image of the study ulcer
- Apply SC. A non-adherent (NA) wound contact dressing and/or an absorbent dressing may be used at Investigator's discretion if required in addition to the compression system.
- Record all dressing use
- Assess for any post-application AEs
- Schedule the next study visit in one week's time

The Run-in Phase ends with TV1 which is also the first visit of the Treatment Phase.

Table 1: Schedule of Events – Run-in Phase

Activity/Assessment	RV1	RV2	RV3	RV4	RV5/TV1
Informed consent	✓				
Assessment of response to geko™ treatment	✓ [∞]				
Ankle-Brachial Index (ABPI) if a valid ABPI reading has not been taken within 8 weeks of RV1	✓				
Confirmation of eligibility	✓				
Medical history	✓				
CWIS, EQ-5D-5L and assessments	✓				
Physical examination and BMI	✓				
Concomitant medications	✓	✓	✓	✓	✓
Assessment of compression bandaging	✓	✓	✓	✓	✓
Study ulcer history	✓				
Study ulcer pain (VAS) assessment	✓	✓	✓	✓	✓
Venous Clinical Severity Score	✓				✓
Assess for AEs		✓	✓	✓	✓
Study ulcer cleaning	✓	✓	✓	✓	✓
Study ulcer surrounding skin assessment	✓				
Study ulcer image(s)	✓ [⌘]				
Study ulcer debridement	✓ [§]				
Application of compression	✓ [¶]				
Assessment for post application AEs	✓	✓	✓	✓	✓
Scheduling of next visit	✓	✓	✓	✓	✓

[∞] Presence of involuntary movement of the lower leg/foot at the maximum tolerable device setting

[§] Study ulcer debridement at Investigator's discretion. N.B. All study ulcer measurements will be performed using the pre-debridement images.

[⌘] If debridement is performed a pre-debridement and a post-debridement image is taken.

[¶] A non adherent (NA) wound contact dressing and/or an absorbent dressing may be used at Investigator's discretion if required in addition to the compression system.

4.2 Treatment Phase

4.2.1 Treatment Visit 1 (TV1) – Prior to Randomization

The assessments on TV1 should be performed in the following order:

- Administer the CWIS and EQ-5D-5L questionnaires in the participant's primary language.
- Administer the study ulcer pain VAS assessment.

- Check for any changes in the participant's health. Any AEs during TV1 prior to randomisation are recorded in the participant's medical history. Following randomisation and during TV2-TV5, update the AE or Serious Adverse Events (SAE) CRF pages as applicable.
- Assess concomitant medications.
- Assess compression bandaging (See Section 9.8)
- Clean the study ulcer.
- Obtain a digital image of the study ulcer (if debridement is planned, this is the Pre-debridement image). N.B. All study ulcer measurements will be performed using the pre-debridement images.
- At the discretion of the Investigator, debride the study ulcer to obtain a clean, granulating ulcer base with minimal adherent slough.
- If applicable, obtain a post-debridement digital image of the study ulcer.
- Verify the participant's continued eligibility (See Sections 3.1.2 and 3.1.3).

If the participant is not eligible, discharge the participant from the study as a screen failure.

If a patient initially fails to meet inclusion/exclusion criteria he/she may later be reconsidered for participation, in which case the patient will be re-consented and assigned a new screening number at the time of re-screening. Patients who fail their first screening attempt may be re-screened once (i.e., up to two screenings) and be enrolled if they meet ALL inclusion and NO exclusion criteria at the second screening visit.

If the patient is eligible, perform the following procedures immediately

4.2.2 Treatment Visit 1 (TV1) – Randomisation and Post-randomisation

Perform the activities below in the following order:

- Randomise the participant. At the randomisation visit, the study ulcer needs to be ≥ 2 cm² and ≤ 30 cm². If other ulcerations are present on the same leg, they need to be at least 2cm away from the study ulcer
- Apply SC.
- Apply appropriate gekoTM to those participants randomised to either gekoTM group.
- Assess for any post-application AE.
- Provide the participant with gekoTM devices as applicable in accordance with the randomisation outcome
- Schedule the next study visit in one week's time.

NB. Each gekoTM device can only be used twice.

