2.1 Efficacy Endpoints

2.1.1 Primary Efficacy Endpoint

The primary efficacy endpoint is linear healing rate (LHR) from TV1 to EOT as compared with LHR from RV1 to TV1. LHR will be calculated by linear regression of the 4 measurements in each phase, with linear wound edge advance being based on the change with respect to time of wound area divided by perimeter, according to Vidal's method (22) [Each participant will be used as his/her own control, i.e. a participant's healing trajectory before introduction of treatment will be compared to his/her healing trajectory after introduction of treatment. Wound area and perimeter will be measured by a blinded independent wound expert using digital images taken at baseline (RV1), first treatment visit (TV1) and at EOT.

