3.1.2 Inclusion Criteria

The inclusion criteria of the study are:

1. Male or female aged ≥ 18 years and able to provide written informed consent.
2. Intact healthy skin at the site of gekoTM device application.
3. Patients who have a chronic venous leg ulcer determined to be due to underlying venous disease following evaluation in a multidisciplinary clinic setting or by a vascular surgeon, GP or Nurse specialist.
4. *A VLU of approximately $\geq 3\text{cm}^2$ and $\leq 39\text{ cm}^2$ at study enrolment i.e. Run In Phase Visit 1 (RVI).* The largest ulcer within the given size range will be designated the study

ulcer and the only one included in the study. If other ulcerations are present on the same leg they have to be more than 2 cm apart if they are separate wounds.

5. Study ulcer (current episode of ulceration in case of ulcer recurrence) has been present for at least 6 weeks but no more than 5 years prior to study entry.
6. Ankle-Brachial Pressure Index (ABPI) of 0.75-1.24 inclusive measured at study entry or within 8 weeks of study entry
7. No active index wound infection for a minimum of 48 hours prior to study entry (i.e. RV1).
8. No systemic antimicrobial treatment for a minimum of seven days prior to study entry prescribed for index wound infection (i.e. RV1).
9. Patient understands and is willing to participate in the study and is able to comply with study procedures and visits.

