5.3 Screen Failures

A patient who has signed a consent form, has been assigned a screening number, but is not randomised is classified as a screen failure. Patient number, demography and reason for screen failure will be collected.

6 Study Treatments

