10.7 Description of Study Endpoints

10.7.1 Primary Efficacy Endpoint

The primary efficacy endpoint for the study is LHR from TV1 to EOT as compared with LHR from RV1 to TV1. LHRs will be measured by a blinded wound expert using digital images at RV1, TV1, EOT, and at HCV if scheduled.

Each participant will be used as his/her own control, i.e. a participant's healing trajectory before commencement of treatment will be compared to his/her healing trajectory after introduction of treatment.

Since significant non-homogeneity may be expected in VLU participants and their respective healing trajectories, a pre-treatment run-in phase will be used to allow each participant to be used as his/her own control, i.e. a participant's healing trajectory before introduction of treatment will be compared to his/her healing trajectory after introduction of treatment. This allows an intra-group pair-wise comparison to evaluate the efficacy of each treatment regimen.

Additionally, for each participant, it enables generation of a treatment healing rate normalised relative to an initial healing rate. Inter-group (albeit un-paired) comparisons based on this normalised value are likely to be more sensitive than comparison of raw healing rates.

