10.10 Analysis Populations

10.10.1 Intent to Treat Population

The Intent-to-Treat (ITT) population is defined as the set of randomised participants who have at least one post-randomisation efficacy assessment for wound healing. The ITT population will be the primary population for the analysis of primary and secondary endpoints.

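### The 2–30 cm² limit at TV1 selects partly on run-in healing, so the within-arm run-in versus treatment change can differ from zero with no device effect

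*Combined protocol and SAP*

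**What the plan says.** **Two size ranges.** Inclusion criterion 4 (section 3.1.2) admits ulcers of about 3 to 39 cm² at RV1. After four weeks of standard care (SC), section 4.2.2 adds: "At the randomisation visit, the study ulcer needs to be ≥ 2 cm² and ≤ 30 cm²".

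**What happens to those outside the range.** Section 4.2.1 says: "If the participant is not eligible, discharge the participant from the study as a screen failure". Section 5.3 says: "Patient number, demography and reason for screen failure will be collected". Section 13.2 confines their case report form to a single page. The primary analysis set (section 10.10.1) is "the set of randomised participants who have at least one post-randomisation efficacy assessment for wound healing", so they are outside it.

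**The endpoint.** The primary endpoint (section 2.1.1) is "linear healing rate (LHR) from TV1 to EOT as compared with LHR from RV1 to TV1", with "linear wound edge advance being based on the change with respect to time of wound area divided by perimeter". TV1 closes one period and opens the other.

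**How it is used.** Of the within-arm contrast, section 10.7.1 says: "This allows an intra-group pair-wise comparison to evaluate the efficacy of each treatment regimen". Section 10.12.1 plans a signed-rank test within each group and a Mann-Whitney test between groups, and does not say which decides the primary result. Section 10.5.2 sizes the trial on the 12h arm's within-arm change alone: mean 0.58, SD 0.97 mm/week, 80% power, two-sided 0.05, 25 participants. Section 3.1.1 gives 60 randomised in total; no allocation ratio is stated. Section 2 gives the objective as geko 12h plus SC against SC alone.

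**The concern.** The area at TV1 is the result of the run-in. A limit on that area is therefore partly a limit on run-in healing, and the treatment phase has no matching limit.

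The two ends of the range work in opposite directions:

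- The lower limit removes small ulcers that healed fast in the run-in. Those left have a low run-in LHR for their underlying rate, and their later LHR tends to look better.
- The upper limit removes large ulcers that healed slowly or grew. Those left have a high run-in LHR, and their later LHR tends to look worse.

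Using each participant as his or her own control does not remove this, because the selection acts on the control period. At stake is the reading of a significant signed-rank test in the 12h arm. That is the only comparison the current sample size supports, section 10.7.1 describes it as evaluating efficacy, and section 10 makes no allowance for selection at TV1.

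**Working it through.** **1. The plan's own figure.** Paired means, inputs from section 10.5.2:

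n = ((1.960 + 0.842) × 0.97 / 0.58)² = 21.95, so 22 by the normal approximation. Adding 1.96²/2 = 1.92 gives 23.87, so 24. Exact noncentral t power is 80.1% at 24 and 81.8% at 25. Dividing 24 by 0.955 for the signed-rank test gives 25.1. The stated 25 is reproduced, for the within-arm change.

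**2. What the limit demands of the run-in.** Assume circular ulcers, r = √(A/π):

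| Area (cm²) | Radius (mm) |
|---|---|
| 2 | 7.98 |
| 3 | 9.77 |
| 30 | 30.90 |
| 39 | 35.23 |

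- 3 cm² at RV1: randomised only if mean radial advance is at most (9.77 − 7.98)/4 = 0.45 mm/week.
- 39 cm² at RV1: randomised only if it is at least (35.23 − 30.90)/4 = 1.08 mm/week.
- Ulcers of about 10–20 cm² are little affected.

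For a circle, area/perimeter = r/2. If LHR is the slope of that ratio, the two thresholds halve to 0.22 and 0.54 mm/week.

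**3. Size of the false change, simulated with no device effect.** The documents supply only the two size ranges and the SD of 0.97. The rest is assumed: circular ulcers, the same mean rate in both phases (values from 0.2 to 1.0 mm/week tried), person-to-person variation in rate, independent phase-to-phase variation giving an SD of change of 0.84 to 0.97, and retention only if TV1 area is 2–30 cm². LHR is radial advance.

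| Assumed RV1 sizes | Mean treatment minus run-in LHR (mm/week) |
|---|---|
| centred on 6 cm² | +0.06 to +0.17 |
| centred on 9–10 cm² | +0.02 to +0.10 |
| centred on 14 cm² | −0.02 to +0.03 |
| centred on 20 cm² or more, or uniform over 3–39 cm² | −0.09 to −0.01 |

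Without the limit the mean change is zero. With 25 or 30 in the arm, the two-sided signed-rank test rejects in about 5% to 14% of trials across these settings, against a nominal 5%. The between-arm Mann-Whitney test stays at about 4% to 6%.

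If LHR is the slope of area/perimeter and the SD of 0.97 is on that scale, the equivalent SD in radius is 2 × 0.97 = 1.94 mm/week and the limit cuts deeper. The false change then ranges from −0.11 to +0.30 mm/week, with false positives of about 4% to 39%. The documents do not settle which scale the 0.97 is on.

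**4. What 60 participants give the randomised comparison.** Assume 1:1 allocation, a difference in mean change of 0.58 (no mean change in SC) and SD 0.97 in each arm:

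- n per arm = 2 × 21.95 = 43.9, so 44 (88 in total) for 80% power.
- At 30 per arm: 0.58 / (0.97 × √(2/30)) − 1.96 = 0.36, power about 64%.
- At 25 per arm: 0.58 / (0.97 × √(2/25)) − 1.96 = 0.15, power about 56%.

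**The case against.** The strongest reply is that the sign is unknown and the effect is mostly small. The two limits oppose each other, and at a median of about 14 cm² they roughly cancel. Even the largest radial value, 0.17, is 0.17/0.58 = 29% of the sizing difference. This stands, and it limits the claim to saying that the contrast can mislead.

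Three details also stand:

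- The 0.45 mm/week threshold is an end-to-end average. Section 2.1.1 specifies a regression on four measurements per phase. An ulcer falling from 3 to 2 cm² in one step mid-phase could show a slope of 0.4 × 1.79 = 0.72 over RV1–RV4.
- The limit must act on a reading at the visit, whereas the analysed area is read by the blinded expert at study end (section 9.9.9). The two should be closely related but are not the same measurement.
- An ulcer that closed in the run-in cannot be treated, so some check at TV1 is unavoidable. The SC within-arm test and the between-group test are already planned.

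Some stronger readings are tempting and are not supported:

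- *That the interim 0.58 is an artefact.* Most settings give far less. The amendment log also dates the 2–30 cm² wording to 28/08/2019, while the sizing calculator was cited in March 2020. Some interim participants may have been randomised before the limit was written in.
- *That 25 participants have less power than stated, after subtracting an assumed artefact.* The limit stays in force, so any shift inside 0.58 would recur in the final data. If 0.58 and 0.97 hold, the planned test still rejects about 82% of the time. The problem is what a rejection means.
- *That 14% is a ceiling on false positives.* It is only the highest value among the radial settings tried.
- *That sharing the TV1 image between the two slopes is a separate source of bias.* Measurement error there has mean zero, and without the limit it leaves the mean change at zero. Whether TV1 enters both slopes is also unclear from the four measurements specified.

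**Conclusion.** The concern holds as a limit on interpretation. Selection at TV1 means that a non-zero within-arm change in the 12h arm is not, on its own, evidence of a device effect. The size rests on assumptions about ulcer sizes, mean rates and variance components that the documents do not give. The radial range is not a bound, and the area/perimeter definition could widen it.

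A reader might infer that the trial's main conclusion is compromised. It need not be. Randomisation follows the limit, so both arms carry the same selection. The SC arm's own change estimates what selection, together with anything else common to both arms, contributes, and the difference between arms removes it. The weakness is confined to sections 10.5.2 and 10.7.1, which size the trial on the contrast that lacks this protection and describe it as evaluating efficacy.

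**What to change.** 1. In sections 10.7.1 and 10.12.1, base the efficacy conclusion on the planned between-group comparison of change, 12h against SC. Report the 12h within-arm change only beside the SC within-arm change and their difference.
2. Delete from section 10.7.1: "This allows an intra-group pair-wise comparison to evaluate the efficacy of each treatment regimen".
3. In section 10.5.2, and where the Synopsis repeats it, state that 25 participants and 80% power apply to the within-arm change only.
4. Report run-in LHR for participants excluded on size at TV1. Section 4.2.1 takes the TV1 image before eligibility is verified, and section 9.9.9 already sends all images to the independent expert.

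The cost is wording in the protocol and SAP, some extra image reading, and a less favourable power statement: about 64% for the between-group comparison at 30 per arm, on the assumptions in step 4 of the working.

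Applying the size limits at RV1 only would remove this selection but would admit some very small ulcers to randomisation. That is a trade-off for the sponsor and is not part of this fix.

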4.2.3 Treatment Phase Visits 2- 4 (TV2 – TV4)

Perform the assessments/activities in the following order:

- Administer the study ulcer pain VAS assessment.
- Check for any changes in the participant's health and update the AE or Serious Adverse Events (SAE) CRF pages if applicable.
- Assess concomitant medications.

- Assess compression bandaging (See Section 9.8).
- Assess study ulcer healing (to be performed by treating PI or designee)

If the study ulcer is 100% re-epithelialised without drainage:

- Obtain a digital image of the study ulcer site.
- Provide appropriate follow-up therapy for the healed ulcer and schedule the participant for a Healing Confirmation Visit (HCV) in a minimum of 7 days.
- Administer the CWIS and EQ-5D-5L questionnaires in the participant's primary language.
- Complete the remaining applicable visit procedures.

If the study ulcer is not 100% re-epithelialised without drainage:

- Clean the study ulcer.
- Check for signs of clinical infection. If clinical diagnosis of infection has been made, the participant should be treated with topical antimicrobials or oral antibiotics in accordance with local best practice. SC, or SC plus either gekoTM treatment will continue at Investigator's discretion.
- Obtain a digital image of the study ulcer (if debridement is planned this will be the pre-debridement image). N.B. All study ulcer measurements will be performed using the pre-debridement images.
- Debride the study ulcer to obtain a clean, granulating ulcer base with minimal adherent slough, at the discretion of the Investigator.
- If applicable, obtain a digital image of the study ulcer (post-debridement image)
- Apply appropriate gekoTM to those participants randomised to either gekoTM group.
- Assess for any post-application AEs.
- Schedule the next study visit in one week's time.

Note that TV4 is the final scheduled study product application.

- Apply SC. A non adherent (NA) wound contact dressing and/or an absorbent dressing may be used at Investigator's discretion if required in addition to SC. All dressing use will be recorded.
- Assess and sign the participant diary card (gekoTM groups only).

4.2.4 Final Treatment Phase Visit (TV5)

Perform the assessments/activities in the following order:

- Administer the CWIS and EQ-5D-5L questionnaires in the participant's primary language
- Administer the study ulcer pain VAS assessment.
- Assess and sign the participant diary card (gekoTM groups only).
- Check for any changes in the participant's health and update the AE or SAE CRF pages if applicable.
- Assess concomitant medications.
- Assess compression bandaging (See Section 9.8).
- Assess study ulcer healing (to be performed by treating PI or designee)

If the study ulcer is 100% re-epithelialised without drainage:

- Obtain a digital image of the study ulcer site.
- Provide appropriate follow-up therapy for the healed ulcer and schedule the participant for a Healing Confirmation Visit (HCV) in a minimum of 7 days.
- Administer the CWIS and EQ-5D-5L questionnaires in the participant's primary language.
- Complete the remaining applicable visit procedures.

If the study ulcer is NOT 100% re-epithelialised without drainage:

- Complete the remaining visit procedures.
- Check for signs of clinical infection.
- Clean the study ulcer.
- Digital image of the study ulcer (if debridement is planned this will be the pre-debridement image). N.B., all study ulcer measurements will be performed using the pre-debridement images.
- Debride the study ulcer to obtain a clean, granulating ulcer base with minimal adherent slough, at the discretion of the Investigator.
- If applicable, obtain a digital image of the study ulcer (post-debridement).
- Provide appropriate follow-up therapy for the non-healed ulcer and exit the participant from the study.

Table 2: Schedule of Events – Treatment Phase

Activity/Assessment	TV1 (pre-rand)	TV1 (post-rand)	TV2	TV3	TV4	TV5 /Final Visit
CWIS and EQ-5D-5L assessments	✓					✓
Study ulcer pain assessment (VAS)	✓		✓	✓	✓	✓
Assess for AEs	✓		✓	✓	✓	✓
Assess concomitant medications	✓		✓	✓	✓	✓
Assess compression bandaging	✓		✓	✓	✓	✓
Study ulcer exudate assessment	✓		✓	✓	✓	✓
Venous Clinical Severity Score						✓
Leg oedema assessment	✓		✓	✓	✓	✓
Study ulcer healing assessment			✓ [∞]	✓ [∞]	✓ [∞]	✓ [∞]
Study ulcer cleaning	✓		✓	✓	✓	✓
Study ulcer margin assessment	✓		✓	✓	✓	✓
Study ulcer surrounding skin assessment	✓		✓	✓	✓	✓
Study ulcer bed appearance	✓		✓	✓	✓	✓
Signs of infection of study ulcer	✓ [¶]		✓ [¶]	✓ [¶]	✓ [¶]	✓ [¶]
Study ulcer image(s)	✓ [⌘]		✓ [⌘]	✓ [⌘]	✓ [⌘]	✓ [⌘]
Study ulcer debridement	✓ [§]		✓ [§]	✓ [§]	✓ [§]	✓ [§]
Confirm eligibility	✓					
Randomisation		✓				
Apply SC		✓	✓	✓	✓	✓
Apply geko™ as per randomisation		✓	✓	✓	✓	
Assess for post-application AEs		✓	✓	✓	✓	✓
Assess and sign the participant diary card (geko groups only)			✓	✓	✓	✓
Provide the participant with the appropriate geko devices as applicable		✓	✓	✓	✓	
Schedule next visit		✓	✓	✓	✓	

[∞] Study ulcer healing assessment to be performed by PI or designee. Participants with 100% re-epithelialisation without drainage will be scheduled for a Healing Confirmation Visit in a minimum of 7 days time.

[¶] If clinical diagnosis of infection has been made, the participant should be treated with topical antimicrobials or oral antibiotics in accordance with local best practice. Study treatment will continue as per Investigator's discretion

[⌘] If debridement is performed a pre-debridement and a post-debridement image is taken. N.B. All study ulcer measurements will be performed using the pre-debridement images.

[§] Study ulcer debridement at Investigator's discretion

